2.2.1. Nonclinical Studies

2.2.1.1. Nonclinical Pharmacology

The SYNB1020 strain was evaluated with relevant comparators in a series of in vitro assays of arginine biosynthesis as well as in vivo studies designed to measure ammonia consumption. Nonclinical evaluation included an antibiotic-resistant strain, SYNB1010, that was designed with the same gene modifications as SYNB1020 except for the nucleotide changes corresponding to

the kanamycin resistance gene. For a comprehensive description of the nonclinical development program, refer to the SYNB1020 Investigator's Brochure.

2.2.1.2. In Vitro Characterization of SYNB1010/SYNB1020

As a biocontainment measure, SYNB1020 and precursor strains were engineered with a deletion of the *thyA* gene encoding thymidylate synthase to create a thymidine auxotroph. At least 2 mM of thymidine was found to be required for continuous growth of these strains, and at lower concentrations the strains grew for a short period of time and then began to die. Concentrations of thymidine in intestinal fluid, urine, and blood are very low (< 0.03 mM). Therefore, SYNB1020 is not expected to grow in intestinal fluids, blood, or urine.

2.2.1.2.1. In Vivo Characterization of SYNB1010/SYNB1020

The distribution of SYNB1010 following oral administration was studied in normal mice. It was found that within 1 hour of oral dosing of mice with 10^{10} colony-forming units (CFU), peak levels of bacteria were found in the distal small intestine and cecum. The cecum and colon remained the sites of highest concentration of bacterial load over the 30 hours post-dosing. Oral dose levels of 10^7 to 10^{10} CFU of SYNB1010 on Days 1 and 2 were evaluated for recovery in mouse feces from Days 1 to 5. Higher doses were associated with higher levels of recovery, with the greatest amounts recovered on Days 2 and 3 after dosing. Complete clearance of detectable SYNB1010 requires longer than 3 days following the last oral dose for dose levels greater than 10^7 CFUs of bacteria.

Following oral dosing of mice with 10^{10} CFU of SYNB1010, SYNB1010 recovered from cecum and colonic contents was metabolically active and converted ammonia to arginine in ex vivo studies at levels similar to those measured in vitro for the strain.

2.2.1.2.2. Pharmacodynamic Studies in Thioacetamide Induced Liver Injury Mouse Model

In vivo efficacy of SYNB1020 was studied in thioacetamide (TAA)-treated BALB/c mice (N=10/group). Following 4 weeks of TAA administration (150 mg/kg 3 times/week) mice were switched to 70% high protein diet for 3 days in order to induce hyperammonemia. SYNB1020 was orally administered at increasing doses. Administration of 1×10^9 to 1×10^{10} CFU of SYNB1020 lowered blood ammonia levels in a dose dependent manner, with statistically significant ammonia reduction at 1×10^{10} CFU of SYNB1020 (from 144 ± 10.9 μ g/dL to 84 ± 11.1 μ g/dL).

2.2.1.2.3. Pharmacodynamic Studies in *spf^{ash}* Mouse Model with Ornithine Transcarbamylase Deficiency

In vivo efficacy of the bacterial strains was studied in the *spf^{ash}* mouse model of ornithine transcarbamylase (OTC) deficiency, a subset of hyperammonemia that results from a defect in the activity of one of the enzymes of the urea cycle.¹⁸ Mice exhibit a deficiency in OTC messenger ribonucleic acid (mRNA), and affected mice exhibit increased blood levels of ammonia observed upon feeding with an extremely protein-rich diet. Mice dosed with SYNB1010 exhibited significantly decreased blood ammonia levels. Hyperammonemic mice dosed with SYNB1010 showed an increased survival benefit.

2.2.1.3. Nonclinical Toxicology

2.2.1.3.1. Nonhuman Primate Study

A non-Good Laboratory Practice (non-GLP) repeat-dose safety and tolerability preclinical safety study in the nonhuman primate (NHP) was conducted. Female cynomolgus monkeys, 2 to 8 years of age, were dosed once daily (QD) for 28 days with SYNB1010 at a maximum dose of 10^{12} CFU/animal followed by a bicarbonate flush. Control animals received bicarbonate solution only. SYNB1010 was well tolerated; no study-compound-related mortality occurred and no test article-related effects were identified on clinical observations, body weight, or clinical pathology assessments including hematology, coagulation, and clinical chemistry. In the SYNB1010-dosed animals, no bacteria were detected in the feces after Day 7 post-dosing.

2.2.1.3.2. 28-day Good Laboratory Practice Mouse Toxicology Study

To evaluate the potential toxicity of SYNB1020, a 28-day, GLP toxicology study was conducted in male and female CD-1 mice. The study evaluated twice daily (BID) oral gavage (PO) dose administration of SYNB1020 for 4 weeks followed by a 2-week recovery period. The maximum dose was 1.56×10^{11} CFU/day, which is the highest feasible dose in this species and corresponds to a human dose of 2.3×10^{14} based on the human and mouse GI volume ratio of 1100.¹⁹ There was no test-article-related mortality, no clinical observations, and no pathological findings on necropsy. Low levels of SYNB1020 DNA were detectable in stomach ileum and colon 24 hours following the last dose but were not detected outside the GI tract (spleen, liver, bladder, gonads) in animals correctly dosed by oral gavage.

2.2.1.4. Summary of the Nonclinical Development Program

In summary, SYNB1020/1010 have been evaluated in a preclinical efficacy and safety program that includes in vitro characterization that demonstrates increased ammonia consumption and arginine production as well as the growth-limiting effect of thymidine auxotrophy. SYNB1020 does not contain any antibiotic resistance genetic markers and has demonstrated susceptibility to a wide range of antibiotics. In vivo, kinetics in cynomolgus monkeys demonstrated that the strain does not colonize and is cleared from the feces within a week following discontinuation of dosing. In the nonclinical safety program, SYNB1020 was evaluated in a GLP toxicology study in mice and a closely related strain, SYNB1010, was evaluated in a non-GLP toxicology study in NHPs. There were no toxicological findings after 28 days of dosing at dose levels of up to 10^{11} CFU in mice and 10^{12} CFU in the NHP.

2.2.2. Clinical Studies

Study SYNB1020-CP-002 represents the second clinical investigation of SYNB1020. One study of SYNB1020 is ongoing in healthy adult male and female volunteers (see [Section 2.2.2.1](#)). In addition, a large body of evidence is available for the clinical safety and efficacy of *E. coli* Nissle, the parent strain of SYNB1020 (see the SYNB1020 Investigator's Brochure).

2.2.2.1. Study SYNB1020-CP-001

Study SYNB1020-CP-001 is an ongoing Phase 1, dose-escalating, randomized, double-blinded study designed to determine the maximum tolerated dose (MTD) of single and multiple doses of

SYNB1020 in placebo-controlled cohorts of male and female healthy adult subjects. As of 30 October 2017, 52 subjects (40 male, 12 female) aged between 21 and 64 years were enrolled in Study SYNB1020-CP-001 and received at least 1 dose of SYNB1020 or matching placebo (Table 1).

Table 1: Study Enrollment in Study SYNB1020-CP-001

Regimen	SYNB1020 Dose	No. Subjects Enrolled (SYNB1020/Placebo)
Single Day	Single dose of 2×10^9 CFU	3/1
Single Day	Single dose of 2×10^{10} CFU	3/1
Single Day	Single dose of 2×10^{11} CFU	3/1
Single Day	Single dose of 2×10^{12} CFU	3/1
Single Day	Multiple dose of 2×10^{12} CFU TID for 1 day	3/1
Single Day	Multiple dose of 5×10^{11} CFU TID for 1 day	3/1
Single Day	Multiple dose of 1×10^{12} CFU TID for 1 day	3/1
Multiple Day	Multiple dose of 2×10^9 CFU TID for 14 days	6/2
Multiple Day	Multiple dose of 2×10^{11} CFU TID for 14 days	6/2
Multiple Day	Multiple dose of 5×10^{11} CFU TID for 14 days	6/2

Abbreviations: CFU = colony-forming unit(s); TID = ter in die (3 times daily)

Note: These preliminary data are based on a cutoff date of 30 October 2017 and may contain unresolved queries.

At the time of data cutoff, subjects in all cohorts had completed at least 72 hours of follow-up after the last dose of SYNB1020/placebo. Upon discharge from the inpatient unit, all subjects continued follow-up as an outpatient until 2 consecutive fecal samples were negative for SYNB1020 by polymerase chain reaction (PCR) analysis. At the time of cutoff, 8 subjects were continuing to be followed, and 44 subjects had completed the study. All subjects who completed study participation had fecal clearance within approximately 4 weeks following the last dose, and no subjects required treatment with antibiotics for positive fecal PCR. Four subjects discontinued the study prematurely due to mild to moderate treatment-emergent adverse events (TEAEs).

Adverse Events

As of 30 October 2017, there were no SAEs or deaths in the study. The most frequently reported TEAEs observed to date in Study SYNB1020-CP-001 were mild to moderate GI disorders, including nausea and vomiting. SYNB1020 was well tolerated in the single ascending dose (SAD) cohorts at single doses up to 5×10^{11} CFU, which was determined to be the MTD. Six subjects (21.4%) experienced TEAEs in the SAD part of the study. Three subjects in the SAD part discontinued dosing due to TEAEs (moderate nausea and vomiting), including 2 subjects in the 2×10^{12} CFU three times daily (TID) cohort and 1 subject in the 1×10^{12} CFU TID cohort. Doses up to 5×10^{11} CFU TID were well tolerated for up to 14 days in the MAD cohorts. Seven subjects (29.2%) experienced TEAEs in the MAD cohorts. One subject in the 5×10^{11} CFU TID cohort discontinued dosing due to TEAEs (mild nausea and vomiting). All TEAEs leading to discontinuation in both the SAD and MAD cohorts occurred during the first day of dosing. Further safety data are presented in the Investigator's Brochure.

2.3. Rationale for the Study

Study SYNB1020-CP-002 represents the second clinical investigation of SYNB1020. Part 1 of the study comprises a sentinel cohort designed to establish the safety and tolerability of SYNB1020 in subjects with cirrhosis. Part 2 of the study is designed to evaluate the safety, tolerability, and pharmacodynamics (PD) of SYNB1020 compared with placebo in patients with hyperammonemia resulting from hepatic insufficiency. The dose of SYNB1020 to be administered in this study will be up to 5×10^{11} CFU given TID immediately after meals for 6 days. The dose level is based on the MTD determined in the Phase 1 single and multiple-ascending dose study (Study SYNB1020-CP-001) in healthy adult volunteers (see [Section 2.2.2.1](#)). The duration of dosing (6 days) is based on the estimate that unmodified EcN requires 2 to 4 days to reach steady state.

Because SYNB1020 is a live biotherapeutic and is therefore susceptible to degradation by stomach acid, subjects enrolled in the study will receive a concomitant histamine-2 receptor (H2) inhibitor. Subjects will receive oral ranitidine (150 mg BID) beginning on Day -5 and for the duration of investigational product (IP) dosing (i.e., through Day 6). Ranitidine was selected for use as it is a widely used over-the-counter therapeutic with a well characterized safety profile and has demonstrated efficacy in increasing gastric pH. Subjects already on a proton pump inhibitor (PPI) will not be switched to ranitidine but will continue their prescribed PPI regimen for the duration of the study.

3. STUDY OBJECTIVES AND ENDPOINTS

3.1. Primary

The primary objective is to evaluate the safety and tolerability of SYNB1020 following multiple doses in hepatic insufficiency and cirrhosis patients. The endpoints related to this objective include the nature and frequency of adverse events (AEs), measurement of vital signs and laboratory assessments (e.g., blood chemistry, complete blood count [CBC], liver function tests, international normalized ratio [INR], and urinalysis), and electrocardiograms (ECGs).

3.2. Secondary

Secondary objectives include evaluation of the following:

- SYNB1020 kinetics in feces (measured with qualitative and quantitative PCR fecal assays) following dosing
- Change from baseline of venous ammonia, including fasting and 24-hour area under the curve (AUC), following SYNB1020 dosing in subjects with hyperammonemia

[REDACTED]

4. STUDY DESIGN

4.1. Study Design Overview

This Phase 1b/2a, randomized, double-blinded placebo-controlled study will evaluate the safety, tolerability, and PD of SYNB1020 in hepatic insufficiency and cirrhosis patients, with dosing of the IP administered in an inpatient unit and subsequent outpatient follow-up for SYNB1020 clearance. Part 1 comprises a sentinel open-label cohort of 6 subjects with cirrhosis and Model for End-Stage Liver Disease (MELD) score <12 to establish the safety and tolerability of SYNB1020. Once the safety and tolerability have been established in Part 1, enrollment will be opened to subjects in Part 2, a randomized, double-blinded, placebo-controlled study in subjects with cirrhosis and hyperammonemia. Approximately 24 to 40 evaluable subjects are anticipated for enrollment in Part 2, with randomization proceeding in a 1:1 ratio to SYNB1020 and placebo.

In Part 1, eligible subjects will be admitted to an inpatient facility for a run-in diet, baseline assessments, IP administration, safety monitoring, and collection of blood, urine, and fecal samples for evaluation of safety, tolerability, and pharmacokinetic and PD evaluations.

In Part 2, subjects may be pre-screened for eligibility based on medical history and a single fasting spot venous ammonia measurement. Eligible subjects with elevated fasting spot venous ammonia will then undergo full screening within 7 days of pre-screening. Eligible subjects will be admitted to an inpatient facility for a run-in diet and 24-hour ammonia profile, and those with an elevated 24-hour ammonia AUC ($>1.2 \times \text{ULN}$) will proceed with randomization, IP administration, safety monitoring, and collection of blood, urine, and fecal samples for pharmacokinetic and PD evaluations.

4.2. Study Dosing Regimens

4.2.1. Dose selection

Dosing is based on data from Study SYNB1020-CP-001, a Phase 1, dose-escalating, randomized, double-blinded study designed to determine the MTD of single and multiple doses of SYNB1020 in placebo-controlled cohorts of male and female healthy adult subjects. The dose administered in this study will be at or below the MTD of 5×10^{11} CFU TID determined in Study SYNB1020-CP-001. The duration of dosing (6 days) was selected to be greater than the time to steady-state for unmodified EcN of 2 to 4 days. Preliminary data for the study are presented in [Section 2.2.2.1](#).

4.2.2. Dietary Regimen and Study Supplements

All subjects will be placed on a weighed research diet calculated based on overall body weight (kg), age, and gender to meet each subject's caloric and protein (2 g/kg/day) requirements based on the dietary reference intakes (DRI).²⁰ This diet will be based on subject preferences as assessed during screening. Diets will include equal caloric and protein content on each day of inpatient monitoring. Subjects will be expected to consume the entirety of their meals and not consume any external foods for the duration of their inpatient study participation. Specifics regarding the diet can be found in the Diet Manual.

In addition, subjects will be administered an H2 inhibitor to reduce stomach acid. Oral ranitidine (150 mg) will be administered BID, 30 to 60 minutes before breakfast and in the evening, for the duration of the inpatient stay (Table 3). Subjects already on a PPI will not be switched to ranitidine but will continue their prescribed PPI regimen for the duration of the study.

4.2.3. Inpatient Monitoring and Investigational Product Administration

Each subject will be admitted to the inpatient unit after an overnight fast on the morning of Day -5. Beginning on Day -5, subjects will initiate a controlled diet and ranitidine. Days -5 through -1 will be a run-in phase to allow for dietary stabilization on the controlled diet. On Day -2, all subjects will undergo baseline 24-hour ammonia profile with 8 measurements (AUC), baseline clinical laboratory sampling and other safety measurements, FibroScan® measurement, and baseline HE grading [REDACTED]. In Part 1, all subjects will receive up to 5×10^{11} CFU of SYNB1020 administered TID immediately after meals from Days 1 through 6 (including mid-day and evening doses on Day 6). Fasting ammonia level will be measured daily. On Day 5, subjects will undergo ammonia AUC assessment. On Day 6, subjects will undergo ammonia AUC assessment, repeat HE grading [REDACTED], as well as 24-hour urine and blood collection. Subjects will be monitored in the inpatient setting for at least 12 hours following completion of dosing, with discharge on Day 7 for clinically stable subjects. Stool samples will be collected daily during the inpatient period. Subjects will be followed for safety and SYNB1020 fecal clearance as outlined in Section 7.5. This cohort is open-label.

In Part 2, only subjects whose screening 24-hour AUC venous ammonia measurement is above $1.2 \times$ the upper limit of normal (ULN) will undergo computer-generated randomization on Day -1 in a 1:1 ratio to receive either up to 5×10^{11} CFU of SYNB1020 or matching placebo administered TID immediately after meals for 6 days. Other assessments will be the same as Part 1. Both subjects and investigators will be blinded to randomized IP assignment.

4.3. Stopping Rules

The Sponsor may stop this study at any time. Investigators will be notified by the Sponsor or its designee if the study is stopped. The occurrence of the following events will require that further enrollment in the study be stopped:

- Any suspected or proven invasive infection (e.g., sepsis or bacteremia) assessed as at least possibly related to the IP.
- Three or more subjects experience the same National Cancer Institute (NCI) Common Terminology Criteria for Adverse Events (CTCAE) grade 3 AE assessed as at least possibly related to study treatment, or two or more subjects experience the same CTCAE grade 4 AE assessed as at least possibly related to the IP.
- Two or more subjects experience SAEs that are considered by the Investigator to be related to the IP.
- Death occurs at any time during the study and is considered by the Investigator to be related to the IP.

- Approximately 6% mortality is observed after 30 days following dosing. This is defined as ≥ 2 deaths observed in 24 subjects or ≥ 3 deaths observed in 40 subjects who have received the IP.
- The Investigator, Medical Monitor, or Sponsor determines that an event or current data warrant stopping the study.

The Sponsor's medical staff, the Contract Research Organization (CRO)'s pharmacovigilance physician and the Lead Investigator will review the data concerning these event(s), along with other available data. Based on the results of their investigation, the Sponsor's medical staff, the CRO's pharmacovigilance physician and the Lead Investigator will determine appropriate follow-up and decide whether the study should be stopped.

If the study is stopped, the events will be investigated, and the study will be closed to further enrollment. Subjects already participating in the study at the time the study is stopped will not receive further IP and will continue the follow-up schedule.

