4.4. Safety Review Committee

A Safety Review Committee comprising the Lead Investigator, Medical Monitor, pharmacovigilance physician, and an external disease expert, as needed, will meet after the completion of Part 1 and ad hoc, as needed, to assess the safety and tolerability of SYNB1020 in subjects with cirrhosis, and to determine whether Part 2 can be conducted safely. The Part 1 safety evaluation will include any available data on AEs, laboratory measurements, vital signs, and ECGs up to 7 days after the last dose of SYNB1020. In Part 2, the Safety Review Committee will meet at predetermined intervals during the study and ad hoc, as needed, to conduct periodic reviews of interim safety data (see [Section 9.7](#)). Further details will be provided in a separate Safety Review Committee charter.

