8.2. Study Discontinuation for Individual Subjects

Subjects must discontinue further IP administration and withdraw from the study for the following reasons:

- Withdrawal of consent;
- Investigator decision;
- Significant noncompliance with protocol procedures;
- >1 missed dose of investigational product
- Necessity for treatment with systemic antibiotics;
- Clinically significant allergy or hypersensitivity reaction to SYNB1020;
- Development of any of the following toxicities:
 - AE of Grade 3 or greater severity according to the NCI CTCAE or life-threatening AE if not covered by CTCAE;
 - Episode of clinically overt HE (West Haven grade 2 or higher; see [Appendix 2](#))
 - QTc interval of > 520 msec or an increase from baseline of > 60 msec confirmed in a repeat test after at least 20 minute;
 - Any of the following laboratory abnormalities:
 - Grade 3 liver enzyme abnormalities and 10-fold ULN for those with normal values at baseline OR a 5-fold increase or 10-fold ULN for those with abnormal values at baseline, whichever is lower;
 - Hemoglobin levels of < 8 g/dL confirmed in a repeat test or requiring blood transfusion;
 - Platelet count of < 20,000/mL confirmed in a repeat test;
 - eGFR < 30 mL/min/1.73m² confirmed in a repeat test;
 - PT > 6.0 sec over ULN or INR level of > 2.3 confirmed in a repeat test;
 - Bilirubin > 5 × ULN confirmed in a repeat test;

- Any other laboratory abnormality of Grade 3 or great severity not covered above and not present at baseline, confirmed in a repeat test.

Subjects may withdraw their consent at any time for any reason without prejudice to their future medical care by the physician or at the institution. If a subject withdraws consent, the date and stated reason for consent withdrawal should be documented. Subject data collected up to the date of consent withdrawal will be included in the analyses.

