9.2.1. Clarification of Serious Adverse Event Definition

- Death is an outcome of an SAE and not an SAE in itself. When death is an outcome, the event(s) resulting in death should be reported (e.g., “pulmonary embolism” with a fatal outcome). The appropriate diagnosis or term should be recorded and assigned severity Grade 5.
- In instances of death due ultimately to the underlying disease, the cause of death should be indicated as the specific event or condition resulting in death to the extent possible. If no appropriate term with a Grade 5 severity in the CTCAE can be identified, then a term should be selected from the CTCAE category “Death”.
- “Life-threatening” means that the subject was at immediate risk of death from the event as it occurred. This does not include an event that might have led to death if it had occurred with greater severity. Grade 4 events (e.g., thrombocytopenia) are not always serious unless they have life-threatening consequences or result in hospitalization.

- Pre-planned or elective hospitalizations including social and/or convenience situations (e.g., respite care) are excluded from SAE reporting. In addition, “admissions” under 23-hour Observation or Emergency Room visits are excluded from SAE reporting; however, such events should still be reported on the appropriate eCRF page.
- Overdose of either SYNB1020 or concomitant medication without any overdose signs or symptoms unless the event meets SAE criteria (e.g., hospitalization) are excluded from SAE reporting; however, such events should still be reported on the appropriate eCRF page.
- SAEs that occur within the safety follow-up period but are related to subsequent therapies are excluded from SAE reporting:
 - Subjects who have completed study dosing or who terminate from study and then undergo subsequent therapies during the safety follow-up period and experience an SAE specifically related to the administration of the subsequent therapy will not have those events reported as SAEs. This exclusion will include “elective” hospitalizations necessary for the administration of such therapies.

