9.7. Review of Safety Data

The designated pharmacovigilance physician in collaboration with the Medical Monitor will be responsible for the ongoing review and evaluation of safety data, including AEs, clinical laboratory data, and any other safety evaluations, for the duration of the study in accordance with the medical monitoring plan. A Safety Review Committee comprising the Lead Investigator, Medical Monitor, pharmacovigilance physician, and an external disease expert, as needed, will meet at predetermined intervals during the study as well as in response to certain clinical outcomes. At each meeting, the Safety Review Committee will review blinded data from the ongoing study and determine whether the study should continue as planned, be modified, or be terminated. ([Section 4.4](#)). For details refer to the separate Safety Review Committee charter.

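### Read literally, the grade-count stopping rule halts enrollment for three related grade 3 cases of one AE but not for two grade 3 cases plus one grade 4

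*Protocol*

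**What the plan says.** Protocol 4.3 lists events that oblige the sponsor to stop further enrollment. The grade-count bullet has two limbs. The first reads "Three or more subjects experience the same National Cancer Institute (NCI) Common Terminology Criteria for Adverse Events (CTCAE) grade 3 AE", with at least possible relation required. The second applies when "two or more subjects experience the same CTCAE grade 4 AE assessed as at least possibly related to the IP". SAP 2.3 repeats the bullet with no addition on higher grades.

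Other bullets in the same list could catch the same subjects. One applies when "Two or more subjects experience SAEs that are considered by the Investigator to be related to the IP". The last lets the Investigator, Medical Monitor or Sponsor call a stop on judgement. A met bullet does not end the study. Sponsor medical staff, the CRO's pharmacovigilance physician and the Lead Investigator review the data, then "determine appropriate follow-up and decide whether the study should be stopped".

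Protocol 8.2 withdraws an individual subject for an "AE of Grade 3 or greater severity according to the NCI CTCAE or life-threatening AE if not covered by CTCAE". In the same list, the liver-enzyme criterion gives grade 3 with no words extending it upward.

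**The concern.** A count-based safety trigger should never become less strict when one event in the set becomes more severe. Here, literally, it does. Take three subjects with the same related grade 3 AE, which obliges a halt. Make one of them grade 4, with that subject's event never recorded at grade 3. The grade 3 count is now two and the grade 4 count is one, so neither limb is met.

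The SAE bullet need not close the gap, because seriousness and grade are separate. Protocol 9.2.1 says "Grade 4 events (e.g., thrombocytopenia) are not always serious unless they have life-threatening consequences or result in hospitalization". The exposed cases are therefore mainly non-serious ones, such as laboratory abnormalities.

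Safety is the primary objective. What is at stake is whether this one pattern brings an automatic halt followed by review, or a review that may or may not lead to a halt.

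**Working it through.** **The rule itself.** The plan attaches no rate, power or error probability to this bullet, so there is no stated figure to reproduce. Let a and b be the numbers of subjects whose worst grade for the same related AE is 3 or 4, with no grade 4 case also recorded at grade 3.

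- As written: halt if a ≥ 3 or b ≥ 2.
- With grade 3 or higher in the first limb: halt if a + b ≥ 3 or b ≥ 2.

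With three affected subjects:

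| a, b | As written | Revised |
|---|---|---|
| 3, 0 | halt | halt |
| 2, 1 | **no halt** | halt |
| 1, 2 | halt | halt |
| 0, 3 | halt | halt |

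Enumerating all pairs of counts shows that the two rules differ only at (2, 1). The revised rule has no reversal.

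**How often the gap would matter.** The documents give no related grade 3–4 rates in cirrhosis, so every rate here is an assumption. Take one AE term, treat all events as related and subjects as independent, and let:

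- p = per-subject probability of a grade 3–4 case
- g = share of those at grade 4 (0.20 or 0.33), so p3 = p(1 − g) and p4 = pg
- s3, s4 = serious shares at grades 3 and 4 (25% and 50%, or 50% and 80%)
- f = fraction of grade 4 cases also recorded at grade 3, which then count in both limbs
- N = 18 SYNB1020 subjects (6 in Part 1 plus 12 of 24 in Part 2, Protocol 5.1 and 10.5), or 26 if Part 2 grows to 40 (6 + 20)

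The gap needs the (2, 1) pattern with fewer than two of the three events serious:

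Loss = C(N,2) × (N − 2) × p3² × p4 × (1 − p)^(N−3) × R × (1 − f), where R = (1 − s3)² + 2·s3·(1 − s3)·(1 − s4).

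R is 0.5625 + 0.1875 = 0.75 for shares of 25%/50%, and 0.25 + 0.10 = 0.35 for 50%/80%.

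Example with N = 18, p = 0.02, g = 0.20, f = 0 and R = 0.75:

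153 × 16 × 0.016² × 0.004 × 0.98^15 × 0.75 = 0.00251 × 0.739 × 0.75 = 0.0014, or 0.14 percentage points.

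Full enumeration including the SAE bullet for this term gives the same difference: trigger probability 0.0091 as written and 0.0105 as revised.

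Percentage points of trigger probability, over both values of g and both pairs of serious shares, with f = 0:

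| Assumed rate p | Lost, 18 SYNB1020, placebo zero | Lost, 26 SYNB1020, placebo zero | Added pauses, 18 SYNB1020 + 12 placebo at equal rate |
|---|---|---|---|
| 1% | 0.01–0.02 | 0.03–0.07 | 0.04–0.10 |
| 2% | 0.06–0.16 | 0.18–0.44 | 0.25–0.63 |
| 5% | 0.6–1.6 | 1.3–3.3 | 1.7–4.2 |
| 10% | 2.3–5.6 | 3.1–7.7 | 3.2–7.9 |

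The last column matters because Protocol 6.1 defines IP to include placebo, so blinded placebo events judged possibly related also count. With f = 0.5 every entry halves.

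**Sensitivity to seriousness.** With 75% of grade 3 and 95% of grade 4 events serious, R = 0.0625 + 0.01875 = 0.08125. For N = 18 and f = 0 the loss falls to about 0.002–0.003 points at 1%, 0.015–0.017 at 2% and 0.15–0.17 at 5%. Related SAEs of other terms would lower it further.

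**The case against.** The strongest reply is that the bullet was meant cumulatively. It is tempting to infer from the wording quoted from 8.2 that this protocol always says so when it means a minimum grade, and hence that 4.3 must be exclusive. The documents do not support that. The liver-enzyme criterion in 8.2 also gives a bare grade 3, evidently as a floor, since no one would withdraw a subject at grade 3 and keep dosing one at grade 4. A cumulative reading of 4.3 is therefore open. What remains is that neither document says a grade 4 case counts toward the grade 3 tally.

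Second, there are backstops even on the literal reading:

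- Each of the three subjects would have to stop IP and withdraw (8.2), and the Sponsor must be told of every withdrawal within 24 hours.
- Two related SAEs of any kind trigger a halt.
- Any of three parties can invoke the discretionary bullet.
- In Part 2, "the Safety Review Committee will meet at predetermined intervals during the study and ad hoc, as needed". Protocol 9.7 adds meetings prompted by particular clinical outcomes, under a charter not included here that may cover this pattern. At each meeting the committee is to "determine whether the study should continue as planned, be modified, or be terminated".

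These points stand and shrink the consequence. They rest on seriousness or judgement, though, and a counted trigger exists so that the halt does not.

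Third, the serious shares may be too low. Dosing is inpatient, prolonged hospitalization makes an event serious, and the general grade 3 description in 9.1.1 includes it. That is fair, and the 75%/95% calculation shows how far the figures fall.

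Finally, the change adds some needless pauses. If events had nothing to do with the drug and occurred at 2% in both arms, pauses would rise by 0.25–0.63 points.

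**Conclusion.** The point holds as a wording defect with a small effect. On its literal text the bullet gives a less protective result for a worse set of events, in exactly one pattern.

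The size rests entirely on assumed rates and serious shares. At 1–2% per subject for one term the loss is about 0.01–0.16 percentage points for 18 SYNB1020 subjects, and less if more events are serious or if grade 4 cases were first recorded at grade 3. The 5–10% rows show range only. Protocol 2.2.2.1 reports no SAEs and mostly mild to moderate gastrointestinal events, though in healthy volunteers, so low rates are plausible.

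A reader might infer that enrollment would carry on unchecked after such a set of events. The documents do not show that: all three cases would reach the Sponsor quickly, and several parties could halt enrollment. Nor is the study's continuation settled by this bullet alone, since a met bullet leads to review.

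This is a cheap improvement to consider. Confidence is moderate, because a cumulative reading may be what was intended.

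**What to change.** In the first limb of the bullet, in both Protocol 4.3 and SAP 2.3, write *the same CTCAE grade 3 or higher AE*. Keep the counts of three and two, and leave the other bullets alone. If the cumulative reading was intended, the edit simply records it.

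The cost is one phrase in each document, with no new data or staff. The downside is slightly more enrollment pauses, some from blinded placebo events. Each would go to the review group already named in 4.3.
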